9.4 HIV Infection

Potential participants who test positive for HIV prior to enrollment will be excluded from the study but will be referred to HIV care and management without delay. Participants who test positive for HIV after enrollment must have study product permanently discontinued by the IoR/designee (if initiated). A participant who is confirmed to be HIV positive during the study will have all follow-up visits discontinued and the participant will be considered terminated from the study as per Section 7.4.1. Participants identified as infected with HIV are managed or referred for management according to the local standard of care. Guidance regarding management and referral for participants confirmed to be HIV-positive can be found in Section 13.10. Sites will not be responsible for paying for HIV-related care.

9.5 Pregnancy

Pregnancy testing will be performed at designated study visits and participants will be encouraged to report all signs or symptoms of pregnancy to study staff. The IoR/designee will counsel any participant who becomes pregnant regarding possible risks to the fetus according to site SOPs. The IoR/designee also will refer the participant to all applicable services; however, sites will not be responsible for paying for pregnancy-related care.

Potential participants who test positive for pregnancy prior to enrollment will be excluded from the study but will be referred to all applicable services. Participants who test positive for pregnancy after enrollment will have study product discontinued (if initiated) and will be terminated from the study as per Section 7.4.2. A participant who is pregnant at study termination will continue to be followed until the pregnancy outcome is ascertained (or, in consultation with the PSRT, it is determined that the pregnancy outcome cannot be ascertained). Pregnancy outcomes will be reported on relevant CRFs; outcomes meeting criteria for SAE reporting also will be reported on the Adverse Event CRF. The study site will make every reasonable effort to contact participants and collect infant outcome up to approximately one year after delivery for those pregnancies that result in live birth.

9.6 Criteria for Early Termination of Study Participation

Participants may voluntarily withdraw from the study for any reason at any time. IoRs/designees also may withdraw participants from the study to protect their safety and/or if they are unwilling or unable to comply with required study procedures, after consultation with the PSRT. Participants also may be withdrawn if CONRAD, USAID, MATRIX, government or regulatory authorities, including the South African Health Products Regulatory Authority (SAHPRA), Kenya Pharmacy and Poisons Board (KPPB), FDA and Office for Human Research Protections (OHRP), or site IRBs/IECs terminate the study prior to its planned end date. Every reasonable effort is made to complete a final evaluation of participants who withdraw or are withdrawn from the study prior to completing follow-up (see details regarding the Early Termination Visit in Section 7.3.5). Study staff members will record the reason(s) for all withdrawals in participants' study records.

10 STATISTICAL CONSIDERATIONS

10.1 Overview and Summary of Design

MATRIX-001 is a Phase 1, multi-site, randomized, placebo-controlled, double-blinded study of daily vaginal administration of the TAF/EVG insert, 20/16 mg. MATRIX-001 will examine the safety, PK, modeled PD, disintegration, and acceptability of inserts containing the combination of TAF and EVG applied vaginally, daily for 3 days, and QOD for 14 days.

10.2 Study Endpoints

Primary Endpoints

Safety

- Changes after dosing:
 - Any TEAE, Grade 2 or higher

Secondary Endpoints

Pharmacokinetics (PK)

- Concentrations of TFV, TAF and EVG in plasma after dosing
- Concentrations of TFV, TAF and EVG in CVF and RF after dosing
- Concentrations of TFV, TFV-DP, TAF and EVG in CVT after dosing

Modeled *in vitro* PD

- Anti-HIV activity in CVF obtained at baseline and after dosing
- Anti-HSV activity in CVF obtained at baseline and after dosing

Acceptability

- Responses to key questions on acceptability (e.g., satisfaction, comfort with insertion, willingness to use) at enrollment and after dosing

Subclinical Safety and Vaginal Microbiome

- Changes in HIV-1 target immune cell phenotype (e.g., CD45, CD68, CD3, and CD1a) and HIV-1 activation/proliferation markers (e.g., HLA-DR) in CVT
- Changes in soluble markers of innate mucosal immunity and inflammatory response in CVF (e.g., IL-1 α , IL-6, IL-10, TNF α , RANTES, MIP-1 α , IP-10, GM-CSF, IL-8, IL-1RA, SLPI, and BD2)
- Changes in the Nugent Score, relative abundance of vaginal microbial species and community state type (CST) measured by 16S RNA sequencing

Exploratory Endpoints

Modeled Tissue PD

- p24 antigen production in CVT infected with HIV-1 *ex vivo*, at baseline and after dosing

10.3 Primary Study Hypothesis

It is hypothesized that there will be no clinically significant change in safety endpoints from baseline when the TAF/EVG Insert, 20/16 mg, is administered vaginally once daily for 3 consecutive days and QOD for 14 days by healthy, non-pregnant, HIV-uninfected adult women at low risk for HIV acquisition.

10.4 Sample Size and Power Calculations

The sample size will be calculated assuming a clinically significant difference between the TAF/EVG insert and placebo of 60% or more. Therefore, the sample size needed to detect such

difference at 5% level of significance and 80% power is 20 (10 participants in each arm) per site for a total of 60 participants to complete. Replacement participants will be enrolled in the event of LTFU.

The sample size estimated above will have enough power to conduct a stratified analysis by study site to show the generalizability of the intervention findings.

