2.5.2 Safety

[figure not shown]
In CONRAD-146, a study conducted in the US, a single dose of TAF/EVG insert administered vaginally was safe and well-tolerated (manuscript under review).²⁷ There were no product related treatment-emergent adverse events (TEAE). There were 8 TEAEs reported by 7 participants (43.8%). The most common TEAE was increased blood glucose, occurring in 3 (18.8%) participants overall. No other TEAE occurred in more than 1 participant. All TEAEs were mild, and none were related to study treatment. TEAEs considered related to study procedure occurred in 2 (12.5%) participants overall. All events of increased blood glucose and events related to the study procedure occurred in Group 1 (4 hour sample collection) (3 [37.5%] and 2 [25.0%], respectively) and did not occur in Group 2 (24 hour sample collection). No treatment-emergent serious adverse effects (TESAE), deaths or TEAEs led to dose interruption, discontinuation of study treatment, or premature withdrawal from the study.

In CONRAD 134, an open-label study conducted in the US that assessed in-vivo disintegration time, safety, and product acceptability of 4 placebo vaginal inserts in 32 women aged 18-50 who were not at risk of pregnancy, placebo inserts were found to be safe, with one mild AE reported that was subsequently assessed as being unrelated to study drug. The optimized insert prototypes were found to disintegrate faster and have higher acceptability over first generation inserts.^{26, 31}

CONRAD 117, conducted in the US, was the first-in-human study of vaginal microbicide inserts using TFV and/or FTC containing vaginal inserts. TEAEs were minimal; only one TEAE met the pre-specified criterion for the safety endpoint, but this event was in the placebo group. Colposcopy and physical exam findings were minimal, as were changes in microflora and systemic laboratory values.²⁶

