10.8.2 Primary Analysis(es)

Product safety will include summaries overall of the incidence of treatment-emergent adverse events, incidence of product-related urogenital adverse events, and incidence of other findings from pelvic examinations (e.g., ulcerations, abrasions, edema, and bleeding). To compare the incidence of TEAEs between the two study arms, Chi-squared test for independence or Fisher's exact test will be used as per the assumptions.

Changes from baseline in clinical laboratory endpoints will be summarized. Shift tables will be produced where relevant.

Evaluation for Study Objectives:

Study objectives will be evaluated by clinical review of descriptive summaries and graphical displays.

Descriptive Statistics:

Categorical variables will be summarized by frequencies and percentages. Continuous variables will be summarized by mean (SD) when found normally distributed. Median (IQR) will be used otherwise. Normality will be assessed graphically by Q-Q plots and statistically by Shapiro-Wilk test for normality. Categorical variables will be summarized by frequency and percentages (e.g. incidence of adverse events).

In addition to descriptive summaries, pharmacokinetic analysis will include time concentration curves for each participant and pooled by sample timepoint group.

To assess for the comparability between the two arms of the study at baseline, t-test or Mann-Whitney test will be used to assess for the differences in continuous variables as appropriate based on the normality assumption. While chi-squared test for independence or Fisher's exact test will be used for categorical variables as appropriate.

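### The 80% power per site in Protocol 10.4 depends on an unstated test and placebo rate; with Fisher's test, two-sided, it is about 64–72% at placebo rates of 5–20%

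*Protocol*

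**What the plan says.** Protocol 10.4 sets the effect: "The sample size will be calculated assuming a clinically significant difference between the TAF/EVG insert and placebo of 60% or more". It then fixes the size needed to detect such a "difference at 5% level of significance and 80% power is 20 (10 participants in each arm) per site for a total of 60 participants", all of them completers, over three sites. It adds: "The sample size estimated above will have enough power to conduct a stratified analysis by study site", and offers this as support for generalizability. It names no placebo event rate, test or sidedness, and it does not say whether the 60% is absolute or relative.

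The primary endpoint (10.2) is binary: any treatment-emergent adverse event (TEAE) of Grade 2 or higher. The planned comparison in 10.8.2 reads "To compare the incidence of TEAEs between the two study arms, Chi-squared test for independence or" Fisher's exact test, with the choice left to the tests' assumptions. No threshold for those assumptions is given. Allocation is 1:1 (10.5), and participants lost to follow-up are replaced rather than allowed for by inflating the number.

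**The concern.** The size is set at site level, 10 per arm, where the large-sample chi-squared test and Fisher's exact test differ noticeably in power. The protocol quotes one power figure without saying which test delivers it, while its analysis section points to a small-sample alternative.

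This is the only operating characteristic stated for the trial, and it concerns the primary safety endpoint. A reader who takes the 80% per site at face value could treat a non-significant comparison at one site as more reassuring than it is.

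**Working it through.** **Inputs.** From 10.4: alpha 5%, power 80%, 10 per arm per site, 30 per arm in total. From 10.2: a binary endpoint. From 10.8.2: chi-squared or Fisher. Assumed, because the protocol does not say: 60% means 60 percentage points, the test is two-sided, and the placebo rate p0 lies between 0% and 40%, the full range that leaves room for a 60-point increase.

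**1. Reproducing the stated number.** With p1 = p0 + 0.60 and p̄ the mean of the two rates, and no continuity correction:

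n per arm = [1.96·√(2p̄(1−p̄)) + 0.8416·√(p0(1−p0) + p1(1−p1))]² / 0.60²

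- 20% vs 80%: (1.386 + 0.476)² / 0.36 = 9.63, so 10.
- 10% vs 70%: (1.358 + 0.461)² / 0.36 = 9.19, so 10.

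For p0 from 0% to 39% the formula gives 8 to 10, so the stated 10 per arm reproduces. The continuity-corrected formula gives 11 to 13.

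**2. Which test applies at 10 versus 10.** The usual convention requires all expected counts to be at least 5. With t events among 20 participants, the expected counts are t/2 and (20 − t)/2 in each arm. Both reach 5 only when t = 10. With a 60-point difference, that has probability 0.6% at p0 = 0%, 12% at 10% and 22% at 20%.

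Even when t = 10, both tests reject at 2 vs 8 (chi-squared p = 0.007, Fisher p = 0.023) and neither rejects at 3 vs 7 (p = 0.074 and 0.179). Enumerating all 121 tables confirms that the rule of chi-squared if expected counts allow, otherwise Fisher, rejects in exactly the same tables as Fisher alone.

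**3. Exact power at 10 per arm for a 60-point difference, two-sided 5%**

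| Placebo rate | Uncorrected chi-squared | Fisher |
|---|---|---|
| 0% | 94.5% | 83.4% |
| 2% | 90.4% | 78.2% |
| 5% | 86.1% | 72.4% |
| 10% | 82.4% | 66.7% |
| 20% | 80.5% | 63.5% |
| 30% | 82.4% | 66.7% |

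Fisher power is 80% at p0 = 1.27%. By symmetry it regains 80% only above 40% − 1.27%, about 38.7%. The gap arises because, with 0, 1 or 2 placebo events, Fisher needs 5, 7 or 8 active events, against 4, 6 or 7 for chi-squared. For 80% power Fisher needs 10 per arm at p0 = 0%, 11 at 5%, and 12 at 10% and 20%.

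**4. One test combined over sites.** A Cochran-Mantel-Haenszel test stratified by three sites (100,000 simulated trials per setting) has power above 99.9% for 60 points at p0 from 0% to 20%. Pooled Fisher at 30 vs 30 has at least 99.8%.

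**5. What 30 vs 30 can detect.** The smallest whole-point increase with at least 80% Fisher power is 26 points at p0 = 0%, 31 at 5% and 34 at 10%.

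**6. Why scale and sidedness matter.** If 60% were a relative increase, per-site Fisher power would be about 3% (20% vs 32%) to 26% (60% vs 96%). If alpha were one-sided 5%, per-site Fisher power for 60 points would be 80.5% to 94.5%.

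**The case against.** The strongest defence is that nothing was miscalculated. Ten per arm follows from the standard formula. The uncorrected chi-squared test, which is named in 10.8.2, has at least 80.5% power at every placebo rate that allows a 60-point increase, and its actual type I error at this size is at most 4.2%. Fisher itself also needs only 10 per arm at 0% vs 60%. The expected-count threshold is a convention that the protocol does not write down. Section 10.8.2 compares the two arms and does not prescribe three separate site tests. It also says objectives are judged by clinical review of descriptive summaries. All of this stands, and it limits the point to an unsupported statement rather than a wrong sample size.

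Three stronger readings are tempting and do not hold:

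- A reader might infer that the by-site claim is simply false. The text allows a single analysis stratified by site, for which power is ample.
- A reader might infer that the 43.8% TEAE rate in 2.5.2 leaves no room for a 60-point increase. That rate counts events of any grade in women who all used active product. All were mild, so none of the 16 met the Grade 2 threshold.
- Conversely, a reader might infer that 0 of 16 shows placebo events are almost absent. Its two-sided 95% upper limit is 1 − 0.025^(1/16) = 20.6%, and it comes from a single dose. The present trial has ten doses, repeated biopsies and an all-cause endpoint.

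**Conclusion.** The concern holds in a limited form. The 80% per site is a property of the uncorrected chi-squared test, or of a placebo rate near zero (or above about 38.7%). It is not a property of the test that 10.8.2 would in practice lead to at 10 versus 10. Under that test, per-site power for 60 points is about 64–72% at placebo rates of 5–20%, a shortfall of roughly 8 to 16 points, equivalent to 1 or 2 more participants per arm per site. The by-site power sentence is unsupported if it means separate tests and amply met if it means one combined test; the text does not say which.

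This rests on an absolute 60 points, a two-sided 5% level and the expected-count-of-5 convention. It should be corrected, but it ranks below a must-fix: the pooled comparison is well powered for the stated effect, and no stated decision depends on a within-site p-value.

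**What to change.** Keep 60 participants and reword 10.4:

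- State that the difference is absolute, on participants with at least one Grade 2 or higher TEAE, with an assumed placebo rate, a two-sided 5% level and the named test.
- Restate per-site power as about 64–72% for 60 points at placebo rates of 5–20%. State the increase that 30 vs 30 can detect with 80% power: about 26, 31 or 34 points at placebo rates of 0%, 5% or 10%.
- Replace the by-site power sentence with one pooled comparison stratified by site, and call within-site results descriptive.
- In 10.8.2, write down the rule that decides between chi-squared and Fisher.

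The cost is a text change and a less favourable stated power per site. No participants or procedures are added.

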10.5 Randomization Procedures

Participants will be randomized (1:1) to receive either combination TAF/EVG or placebo vaginal insert. Participants will be randomized 1:1:1 to one of three timepoint groups for tissue sample collection post dosing.

Participants	Randomization Group
30	TAG/EVG insert
30	Placebo insert

Sample Collection Groups	Timepoints after Dosing
Timepoint group 1	24 hours (7a)
Timepoint group 2	48 hours (7b)
Timepoint group 3	72 hours (7c)

10.6 Participant Accrual, Follow-up and Retention

A sufficient number of women may be consented and undergo assessment procedures in order to have at least 60 (20 in each site) female participants complete the study. All participants that undergo baseline sampling will be included in the analysis. Participants who initiate product use but discontinue the study prior to completion may not re-enroll. Participants who discontinue the study early may be replaced to reach the target of having 60 women with complete study data.

10.7 Blinding

This study will be a double-blinded randomized clinical trial. In case of a severe adverse event and the need to unblind, a pharmacist with access to the randomization code will provide appropriate information.

10.8 Data and Safety Monitoring and Analysis

10.8.1 Study Monitoring

DSMB oversight is not planned for this study. The MATRIX Clinical Trials Hub will conduct interim reviews of study progress, including rates of participant accrual, retention, completion of primary and main secondary endpoint assessments, and study or laboratory issues. The ISP will conduct interim review of a closed safety data report. These reviews will take place approximately every

three months, or as needed. At the time of these reviews, or at any other time, the ISP or PSRT may convene a panel (composed of the ISP, PSRT and protocol statistician[s]) to review study findings. This panel may recommend that the study proceed as designed, proceed with design modifications, or be discontinued. Safety monitoring will be done by the PSRT.

10.8.2 Primary Analysis(es)

Product safety will include summaries overall of the incidence of treatment-emergent adverse events, incidence of product-related urogenital adverse events, and incidence of other findings from pelvic examinations (e.g., ulcerations, abrasions, edema, and bleeding). To compare the incidence of TEAEs between the two study arms, Chi-squared test for independence or Fisher's exact test will be used as per the assumptions.

Changes from baseline in clinical laboratory endpoints will be summarized. Shift tables will be produced where relevant.

Evaluation for Study Objectives:

Study objectives will be evaluated by clinical review of descriptive summaries and graphical displays.

Descriptive Statistics:

Categorical variables will be summarized by frequencies and percentages. Continuous variables will be summarized by mean (SD) when found normally distributed. Median (IQR) will be used otherwise. Normality will be assessed graphically by Q-Q plots and statistically by Shapiro-Wilk test for normality. Categorical variables will be summarized by frequency and percentages (e.g. incidence of adverse events).

In addition to descriptive summaries, pharmacokinetic analysis will include time concentration curves for each participant and pooled by sample timepoint group.

To assess for the comparability between the two arms of the study at baseline, t-test or Mann-Whitney test will be used to assess for the differences in continuous variables as appropriate based on the normality assumption. While chi-squared test for independence or Fisher's exact test will be used for categorical variables as appropriate.

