8.3 Adverse Events Definitions and Reporting Requirements

8.3.1 Adverse Events

An AE is defined as any untoward medical occurrence in a clinical research participant administered an investigational product and which does not necessarily have a causal relationship with the investigational product. As such, an AE can be an unfavorable or unintended sign (including an abnormal laboratory finding, for example), symptom or disease temporally associated with the use of an investigational product, whether or not considered related to the product. This definition is applied to all study participants and is applied beginning at the time of enrollment. The term “investigational products” for this study refers to the TAF/EVG vaginal insert, 20/16 mg. AEs should be assessed for relatedness to study procedure.

Study participants will be provided instructions for contacting the study site to report any untoward medical occurrences they may experience. In cases of potentially life-threatening events, participants will be instructed to seek immediate emergency care. Where feasible and medically appropriate, participants will be encouraged to seek evaluation where a study clinician is based, and to request that the clinician be contacted upon their arrival. With appropriate permission of the participant, whenever possible, records from all non-study medical providers related to untoward medical occurrences may be obtained and required data elements will be recorded on study CRFs. All participants reporting an untoward medical occurrence will be followed clinically until the occurrence resolves (returns to baseline) or stabilizes.

Study site staff will document in source documents and in the study database all AEs reported by or observed in enrolled study participants regardless of severity and presumed relationship to study product. AE severity will be graded per the DAIDS Table for Grading Adult and Pediatric Adverse Events, Corrected Version 2.1, July 2017 and/or Addenda 1 (Female Genital Grading Tables for Use in Microbicide Studies [Dated November 2007]).

For any SAEs that are continuing at a participant’s SEV, the IoR/designee must establish a clinically appropriate follow-up plan for the AE. At a minimum, the SAE must be re-assessed by

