10.8.3 Secondary and Exploratory Analyses

Safety:

To assess for the difference in subclinical safety endpoints between TAF/EVG and placebo group, the incidence of different TEAES will be calculated and risk ratio will be estimated. Chi-squared test or fisher exact test will be used as appropriate. A binary variable will be created for each one of the TEAEs of interest, then Multivariable logistic regression will be used to assess for the difference in the occurrence of TEAEs. In this model the risk ratio will be calculated instead of the odds ratio using Stata command (*oddrisk*).

While for quantitative laboratory safety parameters, mixed-effect design will be used to assess for the changes in these parameters over time within the TAF/EVG and placebo group separately

and will assess for the differences in the laboratory parameters between the TAF/EVG and placebo group.

PK and PD:

PK analysis will include descriptive statistics by sample time point of EVG, TFV, and TAF concentrations for all plasma, CVT, and CVF sample types, in addition to TFV-DP concentrations from CVT samples.

PD endpoints will be summarized using descriptive statistics by time point as well as changes from baseline. Estimates and 95% confidence intervals will be provided. Analysis will include summaries of anti-HIV and anti-HSV activity in CVF, and AUC (Area under the curve) and/or SOFT endpoints will be performed to determine if there is a difference between infection of samples collected at baseline and after treatment. Anti-viral activity in CVF (the change in HIV-1 and HSV infections for samples obtained on treatment vs. baseline) will be summarized.

Changes from baseline in clinical laboratory endpoints will be assessed using paired t test or Wilcoxon signed rank test based on the normality of the data. Repeated measures ANOVA or Friedman test for repeated measures will be used to assess the change from baseline through the endpoint.

Mixed effect-design will be used to compare within and between participants changes for different PK and PD endpoints from baseline to endpoint.

Disintegration and acceptability:

Disintegration endpoints will be summarized descriptively.

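### The sole primary endpoint is TEAEs of Grade 2 or higher, but the primary analysis in 10.8.2 summarizes and tests TEAEs with no grade threshold

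*Protocol*

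**What the plan says.** **Endpoint.** The Protocol Summary, section 4.2 and section 10.2 each list a single primary endpoint: "Any TEAE, Grade 2 or higher".

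**Primary analysis.** Section 10.8.2 opens: "Product safety will include summaries overall of the incidence of treatment-emergent adverse events, incidence of product-related urogenital adverse events", and adds other pelvic examination findings. It then gives the only primary comparison of safety outcomes between arms, a chi-squared or Fisher's exact test: "To compare the incidence of TEAEs between the two study arms". None of these items carries a grade.

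**Secondary analysis.** Section 10.8.3 calculates the incidence of different TEAEs and says "A binary variable will be created for each one of the TEAEs of interest". Again no grade is given.

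**Capture of events.** Section 8.3.1 has sites record all adverse events "regardless of severity and presumed relationship to study product", and each is graded on the DAIDS tables.

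**Earlier experience.** Section 2.5.2 reports that in the sponsor's single-dose study 7 of 16 women (43.8%) had 8 TEAEs between them: "All TEAEs were mild, and none were related to study treatment".

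**The concern.** The variable defined in 10.2 and the variable tested in 10.8.2 differ by a severity threshold. A statistician who follows 10.8.2 literally counts every woman with any TEAE, including Grade 1.

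That matters in this trial because mild events are likely in both arms. The only earlier data on this product show 7 of 16 women with a TEAE, all mild. Section 13.4.1 expects soreness and spotting after biopsy, and both arms have post-dose biopsies at Visits 4 and 7. If such events are about equally frequent in the two arms, they pull the two any-grade proportions together and make a Grade 2+ excess harder to see.

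Leaving the grade unstated also leaves room to choose between the two variables once results are known.

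**Working it through.** **1. Does TEAE in 10.8.2 mean Grade 2 or higher?** The protocol's own usage says not.
- Section 2.5.2 calls the events of the single-dose study TEAEs and says that all were mild.
- The same section says of another sponsor study that only one TEAE met the criterion for its safety endpoint. It thus separates a TEAE from a TEAE that counts towards an endpoint.
- Section 8.3.1 records all severities.
- A Grade 2 threshold appears in the eligibility criteria (5.3), the product-hold rule (9.3) and the endpoint lists, but nowhere in 10.8.

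**2. Does the sample size settle it?** No. Section 10.4 gives 10 per arm per site for a 60% difference at 5% significance and 80% power. That figure reproduces with the pooled two-proportion formula

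n = [1.96·√(2p̄(1−p̄)) + 0.84·√(p₁(1−p₁)+p₂(1−p₂))]² / (p₂−p₁)².

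With an assumed placebo rate of 10%, so 10% v 70%: (1.96·√0.48 + 0.84·√0.30)² / 0.36 ≈ 9.2, rounded up to 10. Assumed placebo rates from 0 to 40% give 8 to 10. Section 10.4 names neither the endpoint nor the placebo rate, so it does not show which variable was meant.

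**3. How much could the choice matter?** The protocol states no Grade 2+ rate, so every such rate here is an assumption. The inputs are:
- 30 per arm (10.5) and a two-sided 5% level (10.4 gives 5% but not the sidedness).
- Uncorrected chi-squared test, or Fisher's exact test if an expected count is below 5.
- Grade 1 background m, equal in both arms and independent of Grade 2+ events. The central value is 44% (7/16); the range is 20% to 60%.

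With g the Grade 2+ rate in an arm, the any-grade rate is 1 − (1−m)(1−g).

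For g = 20% v 2% and m = 44%:
- Active: 1 − 0.56 × 0.80 = 55.2%.
- Placebo: 1 − 0.56 × 0.98 = 45.1%.
- The difference falls from 18 to 10.1 points.

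Power by exact enumeration of all 31 × 31 outcomes:

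| Grade 2+ rates (assumed) | Background m | Power, Grade 2+ | Power, any grade |
|---|---|---|---|
| 20% v 2% | 20% | 42% | 23% |
| 20% v 2% | 44% | 42% | 13% |
| 20% v 2% | 60% | 42% | 9% |
| 30% v 5% | 44% | 69% | 20% |
| 30% v 0% | 44% | 92% | 26% |

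**4. What if the product also causes Grade 1 events?** Keep Grade 2+ at 20% v 2%.
- Grade 1 at 64% v 44%: the any-grade rates are 71.2% v 45.1%, and power is 54%.
- Grade 1 at 50% v 30%: the any-grade rates are 60.0% v 31.4%, and power is 62%.

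Both exceed the 42% on Grade 2+. The direction of the effect therefore depends on whether the product itself adds mild events.

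**The case against.** **Omission is not contradiction.** Section 10.8.2 does not say any grade. It is headed as the primary analysis, and the chapter has one primary endpoint, so TEAEs could be shorthand for it. A SAP that is not shown might also say so. This stands as far as it goes: a reader might infer that the primary endpoint is never analysed, and the documents do not support that. What they support is that no analysis in the protocol is specified for it. The shorthand reading runs against the protocol's own use of TEAE, and since the protocol did choose to state its primary test, the text should match its endpoint.

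**The test does not decide the trial.** Section 10.8.2 has objectives judged by clinical review of descriptive summaries. Grade 2+ events are grounds for a product hold (9.3), and the safety review team meets about monthly (8.2). This limits the consequence: a non-significant any-grade test would be unlikely to hide a marked Grade 2+ excess. It does not supply the missing comparison, because the summaries have no grade threshold either and the routine safety reports are blinded to arm (8.1).

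**The dilution is assumed.** A reader might infer that mild events will swamp the comparison. That is not established.
- The 44% comes from 16 women without a placebo arm.
- Three of the seven affected women had raised blood glucose, which is not among the chemistries in 7.10.
- Section 13.4.1 lists local irritation, itching and discharge as product risks, so a Grade 1 excess on active is plausible, and step 4 shows that it can favour the any-grade test.
- At a Grade 2+ difference of 60 points (65% v 5%, 44% background), the any-grade test at 30 v 30 still has 79% power.

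**Section 10.8.3.** It is tempting to ask for the same threshold there. Nothing in the protocol requires a secondary or exploratory analysis to carry it, and imposing it could hide mild local-irritation signals.

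**Conclusion.** The concern holds as a mismatch between endpoint and analysis. The sole primary endpoint has a Grade 2 threshold; the primary summaries and the primary between-arm test of TEAEs do not; and nothing in 10.8 is specified for the Grade 2+ endpoint. This rests on the text alone and needs no assumption.

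The size is illustrative. With an equal and independent Grade 1 background of 20% to 60% and Grade 2+ rates of 20% v 2%, power falls from 42% to between 23% and 9%. The loss depends on those assumed rates and on the product causing no Grade 1 excess.

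**What to change.** In 10.8.2, state:

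> The primary comparison is the number and proportion of participants in each arm with at least one TEAE of Grade 2 or higher (section 10.2). TEAEs of any grade are tabulated by arm and maximum grade as supportive information.

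Leave the secondary analyses in 10.8.3 unrestricted by grade. If a SAP exists, check that its primary analysis carries the same definition.

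The cost is a short wording change. Severity is already graded for every adverse event, so no procedure, form or sample size changes.
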